7.2.3 Analysis of the physician and patient populations

The analyses of the primary and secondary objectives will be performed on the Analysis Population.

7.2.3.1 Analyses of primary objectives:

To describe medical practices in patients with GCA, the following endpoints will be described on the analysis population:

Patient journey

- » Proportions of each physician who referred the patient
- » Proportions of each physician who follows the patient for his/her GCA (internist/rheumatologist)
- » Time between signs/symptoms and diagnosis: described as quantitative variable and as qualitative variable. (early diagnosis / diagnosis in the standard time / late diagnosis)

The 3 endpoints will be described overall and by subgroups: the first 2 endpoints will be described by time between signs/symptoms and diagnosis (qualitative variable) and the 1st and 3rd endpoints will be described by type of physicians who follows the patient.

Diagnostic mean

- » Proportions of each diagnostic method used

The diagnostic mean will be described overall, by time between signs/symptoms and diagnosis (qualitative variable), and by type of physicians who follows the patient.

Previous and on-going specific GCA treatments since diagnosis

- » Previous and on-going specific GCA treatments since diagnosis

Treatments will be coded using the WHO Drug medicine dictionary (ATC codes). They will be described overall and by type of physician who follows the patient.

7.2.3.2 *Analyses of secondary objectives*

The analysis of the secondary objectives will be performed on the analysis population.

Description of comorbidities related to GCs and associated treatments

- » Current and past comorbidities of GCA patients (comorbidities related to GCs) will be coded using the medical dictionary MedDRA®. They will be described overall and by type of physicians who follows the patient.
- » Treatments in patients with comorbidities related to GCs will be coded using the WHO Drug medicine dictionary (ATC codes). They will be described overall and by type of physician who follows the patient.

Description of GCA characteristics

- » Time between diagnosis and inclusion will be described as quantitative variable and as qualitative variable (patient newly diagnosed or not: incident or prevalent case)
- » Proportion of incident patients: patients with a diagnosis of GCA \leq 6 weeks from inclusion
- » Proportion of prevalent patients: patients with a diagnosis of GCA $>$ 6 weeks from inclusion.

The following endpoints will be described overall and by type of patient (prevalent/incident), by time between signs/symptoms and diagnosis (qualitative variable), and by type of physicians who follows the patient:

- » GCA duration
- » Initial presentation: proportions of patients with cranial GCA, PMR, extracranial GCA, ESR/CRP, general signs
- » Clinical form
 - Proportion of patients with relapse and number of relapse,
 - Proportion of patients with recurrence and number of recurrences,
 - Dose of GCs-dependence
 - Proportion of patients with GCA complications.

Analysis of potential factors associated to relapse will be performed using logistic regression. The associated factors will be defined in the SAP.

- » GCA activity
 - Proportions of each clinical signs/symptoms of GCA activity

- Scores of the patient and physician global arteritis activity VAS (quantitative variable)

The concordance between the scores of the patient and physician global arteritis activity VAS will be evaluated using the kappa coefficient.

The potential factors associated with the increase of the global arteritis activity will be studied.

Description of the health status of GCA patients

» SF-36 questionnaire

The SF-36 is a self-report, 36 item survey measuring health-related quality-of-life. The SF-36 consists of eight scaled scores. A score ranging from 0 (indicating the worse health status) to 100 (indicating the best health status) is assigned for each domain. Scores and missing data of the SF-36 were handled according to the user's manual. The score for each item of SF-36 will be presented (in quantitative) as well as the total score for each domain.

» EQ5D-3L questionnaire

The EQ5D-3L consists of five questions relating to five dimensions of health. Respondents indicate which of a possible three statements best describe their current health state for each dimension. Each dimension has 3 levels: no problems, some problems, extreme problems. Respondents are asked to repeat this process for the five dimensions by indicating one level for each dimension, giving rise to scores ranging from 1 to 3, with scores of 3 on each dimension indicating the most severe impairment. Binary variables will be computed for each dimension dichotomising the levels into 'No problems' (level 1) and 'Problems' (levels 2 and 3). Perceived current health state will be measured by asking respondents to indicate their current health state on a VAS with endpoints labelled 0 'Worst imaginable health state' and 100 'Best imaginable health state. The score for each item of EQ5D-3L will be presented (in qualitative variable at 2 and 3 modalities for 5 dimensions and in quantitative for VAS).

» FACIT-Fatigue

FACIT-Fatigue is a patient-reported rating scale consisting of 13 items that yields a summed total score ranging between 0 and 52 (52= less fatigue).

The score for each items of FACIT-Fatigue will be presented (in qualitative variable) as well as the total score (quantitative variable).

Description of physician and patient characteristics

» Description of physicians

The analysed data will be recorded by the physician in the eCRF.

The population of physicians in the study will be described overall, in terms of demographic parameters (geographic location, number of years of practice, year of medical school graduation), medical specialty, status of the health institution (public hospital, private hospital, both hospital and office-based, other) and number of GCA diagnosis within the previous year.

» Description of patients

Demographic data (age, gender, smoking status) and body mass index will be described overall and by type of physician who follows the patient.

Current and past comorbidities of GCA patients (significant past and concomitant diseases) will be coded by the medical dictionary MedDRA®. They will be described overall and by type of physician who follows the patient.

Treatments will be coded using the WHO Drug medicine dictionary (ATC codes). They will be described overall and by type of physician who follows the patient.

7.2.4 *Schedule for data analysis*

The final analyses will be performed after the database lock and are planned for January 2019.

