2.2 Secondary objectives

The secondary objectives of this study are:

- » To describe comorbidities related to GCs and associated treatments
- » To describe GCA characteristics in terms of GCA duration, initial presentation, clinical form and GCA activity
- » To describe the health status of GCA patients
- » To describe physician and patient characteristics

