5.5.2 Description of GCA characteristics

First the following parameters will be presented:

- Time between diagnosis and inclusion will be described as quantitative variable (months) ([APPENDIX](#))
- Type of patient
 - Proportion of incident patients (newly diagnosed): patients with a diagnosis of GCA \leq 6 weeks from inclusion
 - Proportion of prevalent patients (not newly diagnosed): patients with a diagnosis of GCA $>$ 6 weeks from inclusion.

Then the following endpoints will be described overall and by type of patient (prevalent/incident), by type of diagnosis (time between the first medical events related to GCA and diagnosis to GCA as qualitative variable in 3 classes early/in standard time/late diagnosis), and by type of physicians who follows the patient.

- Initial presentation:
 - Proportion of patients with at least one cranial manifestation at diagnosis and the proportion of each symptom of this family (Headaches/ Scalp sensitivity / Anomalies of the temporal arteries (temporal artery sensitivity or decreased pulsation) / Ischemia-related vision impairment and-or loss / Mouth pain or jaw claudication during mastication / Stroke or transient ischemic attack (TIA) / Other)

Listing of Ischemia-related vision impairment / loss and other cranial manifestation at diagnosis will be presented.

- Proportion of patients with at least one PMR symptom at diagnosis and the proportion of each symptom of this family (Morning stiffness and-or pain in the shoulder girdle/ Morning stiffness and-or pains in the pelvic girdle/ Inflammatory arthromyalgia/ Peripheral arthritis/ Other)

A listing of other PMR symptom will be presented.

- Proportion of patients with at least one extracranial event (excluding PMR) at diagnosis and the proportion of each symptom of this family (Thoracic or abdominal aortic aneurysm and-or dilatation/ Aortitis and-or involvement of aortic branch(s) in imaging/ Angina and-or Myocardial infraction/ Claudication of an upper limb and-or claudication of a lower limb/ Sign of subclavian stenosis (asymmetry of pulse, blood pressure, subclavian murmur)/ Other)

A listing of other extracranial events (excluding PMR) will be presented.

- Value of ESR (mm/1st h) and CRP (mg/L) at diagnosis and at inclusion.
- Proportion of patients having abnormal value of ESR (ESR $>$ 50 mm/h)/CRP (CRP $>$ 25 mg/L) at diagnosis
- Proportion of patients having abnormal value of ESR (ESR $>$ 50 mm/h)/CRP CRP $>$ 25 mg/L) at inclusion

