9.3.2 Description of GCA characteristics

Table 14 - Efficacy analysis – Description of GCA characteristics - Analysis population (N=XX)

Parameter	Statistics	Total (N=XX)
Time between diagnosis and inclusion (months)	Mean SD Median [Q1 ; Q3] [Min ; Max] Filled, n(%) Missing, n(%)	
Type of patient * Incident Prevalent	n(%) n(%) Filled, n(%) Missing, n(%)	

*Incident if diagnosis of GCA ≤6 weeks from inclusion
Prevalent if diagnosis of GCA >6 weeks from inclusion
The percentages are calculated compared to filled data
STUDY : CHUGAI-ARTEMIS - Edition date: DDMMYY
Pgm : EFFICACY\GCA.SAS

Table 15 - Efficacy analysis – Initial presentation of GCA - Analysis population (N=XX)

Parameter	Statistics	Total (N=XX)
Patient with at least one cranial manifestation at diagnosis No Yes	n(%) n(%) Filled, n(%) Missing, n(%)	
Cranial manifestation* Headaches Scalp sensitivity Anomalies of the temporal arteries Ischemia-related vision impairment and-or loss Mouth pain or jaw claudication during mastication Ischemia-related vision impairment and-or loss Stroke or transient ischemic attack (TIA) Other	n(%) n(%) n(%) n(%) n(%) n(%) n(%) n(%)	
Patient with at least one PMR symptom at diagnosis No Yes	n(%) n(%) Filled, n(%) Missing, n(%)	
PMR symptom * Morning stiffness and-or pain in the shoulder girdle Morning stiffness and-or pains in the pelvic girdle Inflammatory arthromyalgia Peripheral arthritis/ Other	n(%) n(%) n(%) n(%) n(%)	
Patient with at least one extracranial event (excluding PMR) at diagnosis No Yes	n(%) n(%) Filled, n(%) Missing, n(%)	
Extracranial event (excluding PMR)* Thoracic or abdominal aortic aneurysm and-or dilatation Aortitis and-or involvement of aortic branch(s) in imaging Angina and-or Myocardial infraction Claudication of an upper limb and-or claudication of a lower limb Sign of subclavian stenosis	n(%) n(%) n(%) n(%) n(%)	

Table 15 - Efficacy analysis – Initial presentation of GCA - Analysis population (N=XX)

Parameter	Statistics	Total (N=XX)
Other	n(%)	
Value of ESR (mm/1st h) at diagnosis	Mean SD Median [Q1 ; Q3] [Min ; Max] Filled, n(%) Missing, n(%)	
Value of ESR (mm/1st h) at diagnosis in classes ≤50 mm/h >50mm/h	n(%) n(%) Filled, n(%) Missing, n(%)	
Value of ESR (mm/1st h) at inclusion	Mean SD Median [Q1 ; Q3] [Min ; Max] Filled, n(%) Missing, n(%)	
Value of ESR (mm/1st h) at inclusion in classes ≤50 mm/h >50mm/h	n(%) n(%) Filled, n(%) Missing, n(%)	

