Value of CRP (mg/L) at diagnosis	Mean SD Median [Q1 ; Q3] [Min ; Max] Filled, n(%) Missing, n(%)	
Value of CRP (mg/L) at diagnosis in classes ≤25 mg/L >25 mg/L	n(%) n(%) Filled, n(%) Missing, n(%)	
Value of CRP (mg/L) at inclusion	Mean SD Median [Q1 ; Q3] [Min ; Max] Filled, n(%) Missing, n(%)	
Value of CRP (mg/L) at inclusion in classes ≤25 mg/L >25 mg/L	n(%) n(%) Filled, n(%) Missing, n(%)	
Patient with at least one general signe at diagnosis No Yes	n(%) n(%) Filled, n(%) Missing, n(%)	
Clinical signs and symptoms* Fever>38°C Weight loss Alteration of the general condition	n(%) n(%) n(%)	
If weight loss: value of weight loss (%)	Mean SD Median [Q1 ; Q3] [Min ; Max] Filled, n(%)	

Table 15 - Efficacy analysis – Initial presentation of GCA - Analysis population (N=XX)

Parameter	Statistics	Total (N=XX)
	Missing, n(%)	

* multiple response possible
 PMR : PolyMyalgia Rheumatica
 ESR : Erythrocyte Sedimentation Rate
 CRP : C Reactive Protein
 The percentages are calculated compared to filled data
 STUDY : CHUGAI-ARTEMIS - Edition date: DDMMYY
 Pgm : EFFICACYGCA.SAS

This table will be presented by type of patient (prevalent/incident), by type of diagnosis and the physician who follows the patient.

Listing 4 : Specification of Ischemia-related vision impairment / loss at diagnosis (N= XX)

Patient ID	Type of patient	Type of diagnosis	Physician who follows the patient	Specification of Ischemia-related vision impairment/loss

STUDY : CHUGAI-ARTEMIS - Edition date: DDMMYY
 Pgm : EFFICACYGCA.SAS

Listing 5 : Specification of other cranial manifestation at diagnosis (N= XX)

Patient ID	Type of patient	Type of diagnosis	Physician who follows the patient	Specification of other cranial manifestation

STUDY : CHUGAI-ARTEMIS - Edition date: DDMMYY
 Pgm : EFFICACYGCA.SAS

Listing 6 : Specification of other PMR symptom at diagnosis (N= XX)

Patient ID	Type of patient	Type of diagnosis	Physician who follows the patient	Specification of other PMR symptom

STUDY : CHUGAI-ARTEMIS - Edition date: DDMMYY
 Pgm : EFFICACYGCA.SAS

Listing 7 : Specification of other extracranial events (excluding PMR) at diagnosis (N= XX)

Patient ID	Type of patient	Type of diagnosis	Physician who follows the patient	Specification of other extracranial events

STUDY : CHUGAI-ARTEMIS - Edition date: DDMMYY
Pgm : EFFICACYGCA.SAS

Listing 8 : Specification of other initial characteristics related to GCA at diagnosis (N= XX)

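### GCA duration, an undefined secondary endpoint that the protocol wants described by three subgroups, has no subgroup output in the SAP, and the omission is not declared

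*Protocol*

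**What the plan says.** Protocol 2.2 names duration in a secondary objective: "To describe GCA characteristics in terms of GCA duration, initial presentation, clinical form and GCA activity". Section 6.2 lists GCA duration as a secondary endpoint, separate from the proportions of incident and prevalent patients.

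Protocol 7.2.3.2 has two blocks for these characteristics. The first contains time between diagnosis and inclusion and the incident and prevalent proportions, with no subgroup instruction. The second opens with "The following endpoints will be described overall and by type of patient (prevalent/incident), by time between signs/symptoms and diagnosis (qualitative variable"). The same sentence adds following physician as a third breakdown. GCA duration is the first item in this block, followed by initial presentation, clinical form and GCA activity.

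SAP 5.5.2 also has two blocks. The first contains "Time between diagnosis and inclusion will be described as quantitative variable (months") and the incident and prevalent proportions. The second begins "Then the following endpoints will be described overall and by type of patient", adds delay class and following physician, and goes straight to initial presentation, clinical form and GCA activity. GCA duration is not in it.

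The output shell is "Table 14 - Efficacy analysis – Description of GCA characteristics - Analysis population (N=XX"), with two rows and one Total column. SAP 5.6 declares one departure from the protocol, on treatments for glucocorticoid-related comorbidities.

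**The concern.** A protocol-specified description of a named secondary endpoint disappears between the two documents, and the section meant to record such changes does not mention it.

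The gap matters because of what remains. Eligibility (Protocol 4.2.1) admits newly diagnosed and long-standing patients with no upper limit on time since diagnosis. SAP 5.5.2 then describes by subgroup several quantities that can only grow with time since diagnosis: ever having relapsed, number of relapses, number of steroid kinetics, cumulative glucocorticoid dose and GCA complications. If internists' patients have had the disease longer than rheumatologists' patients, or late-diagnosed patients differ from early-diagnosed ones in time since diagnosis, these quantities will differ between the groups even where practice and disease course are the same. A reader of the planned summary tables could not see whether that was so.

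**Working it through.** **1. Is any duration measure described by subgroup?**

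- Protocol 7.2.3.2: yes. GCA duration is to be described overall, by incident/prevalent status, by delay class and by following physician.
- SAP 5.5.2: no. Time between diagnosis and inclusion comes before the subgroup rule, and nothing called GCA duration comes after it.
- SAP Table 14: one Total column.
- SAP 5.6: silent on the point.

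**2. Does it matter whether the two duration terms mean the same thing?** Neither document says. There are two readings:

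- If they are the same variable, the SAP reports it overall and loses three required breakdowns.
- If they differ, GCA duration is undefined and absent from the SAP altogether.

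Either way the protocol's subgroup output is missing.

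**3. Would another planned output fill the gap?**

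- Table 4 (by following physician) and Table 33 (patient characteristics, repeated by following physician) contain neither time since diagnosis nor incident/prevalent status.
- Table 3 (by delay class) contains only referring and following physician.
- The relapse model in SAP 5.5.2 has incident/prevalent status as a binary factor, but neither continuous duration nor following physician.
- SAP section 8 says that derived data will be included in the listings. No listing shell has a column for time between diagnosis and inclusion, and a listing is not a summary.

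**4. Scale.** The documents give no relapse rate and no duration by subgroup, so there is no stated figure to reproduce and every input here is an assumption. Take a constant relapse rate r per year, the same in both groups, and give every patient in a group the same duration t in years. The proportion ever relapsed is 1 − exp(−r × t). With t = 2 v 1 (24 v 12 months):

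| r per year | t = 2 | t = 1 | Gap (points) |
|---|---|---|---|
| 0.2 | 1 − exp(−0.4) = 33.0% | 1 − exp(−0.2) = 18.1% | 15 |
| 0.3 | 1 − exp(−0.6) = 45.1% | 1 − exp(−0.3) = 25.9% | 19 |
| 0.5 | 1 − exp(−1.0) = 63.2% | 1 − exp(−0.5) = 39.3% | 24 |

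A second set of assumptions uses rates of 0.1, 0.2 and 0.4 per year and durations of 1 v 2, 1.5 v 3 and 2 v 4 years. The smallest gap is at 0.1 per year and 1 v 2 years: 18.1% − 9.5% = 8.6 points. The largest is at 0.4 per year and 1.5 v 3 years: 69.9% − 45.1% = 24.8 points. With equal durations the gap is zero.

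**5. Which of the three breakdowns matter most?** Incident status is defined by duration. The 6-week limit is 42/30.4375 = 1.38 months, so a duration table by incident/prevalent status largely restates the definition. The informative breakdowns are delay class and following physician.

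**The case against.** The strongest reply is that the SAP follows the protocol for the variable it reports. Protocol 7.2.3.2 itself places time between diagnosis and inclusion ahead of the subgroup rule, and SAP 5.5.2 and Table 14 keep that order. This is right. A reader might infer that the SAP removed this variable from the subgroup list, but it was never there. What was dropped is the separately listed and undefined GCA duration.

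A second reply concerns the shells. Table 15 carries the note "This table will be presented by type of patient (prevalent/incident), by type of diagnosis and the physician who follows the patient" and Table 14 does not, but Tables 16 to 20 have no such full note either. Its absence under Table 14 therefore proves little. The point rests on the text of 5.5.2, which promises the breakdowns for the content of Tables 16 to 20 and does not promise them for duration.

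Third, a reader might infer that subgroup differences cannot be separated from disease duration because of this omission. The documents do not support that. The protocol's own table would show an imbalance without adjusting for it, so full compliance would not separate the two either. Nor do the documents show that an imbalance exists.

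Fourth, it is tempting to say that cumulative glucocorticoid dose rises with duration as the relapse proportion does. The protocol's introduction describes high initial dosing followed by gradual tapering. Without relapse, dose then accumulates mostly early, so the relapse illustration should not be carried over to dose.

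Finally, the study is descriptive and plans no formal subgroup comparison. That limits the severity. But the subgroup tables are what the study delivers, and readers will compare their columns.

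**Conclusion.** The point holds as an undeclared omission with a moderate consequence for interpretation. GCA duration is a named secondary endpoint without a definition, and the SAP provides none of the three subgroup descriptions that the protocol asks for. Outcomes that accumulate with time are still shown by delay class and following physician, so an imbalance in duration that might explain part of a difference would be invisible in the planned summary tables.

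The discrepancy follows from the documents alone. The size does not: the gaps of 15 to 24 points in ever-relapsed assume equal constant rates of 0.2 to 0.5 per year and durations of 24 v 12 months, and they show only that the effect need not be small. It should be corrected before the analysis is run, but it does not undermine the study's primary objective.

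**What to change.** In SAP 5.5.2, define GCA duration as time between diagnosis and inclusion, using the derivation in Appendix item (3), and add it to the endpoints described by subgroup. Repeat Table 14 at least by delay class and by following physician, and by incident/prevalent status because the protocol requires it. The alternative is to declare and justify the omission in SAP 5.6.

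The cost is a few lines of SAP text and up to three repeats of a two-row table. The variable is already derived for each patient, so no new data are needed. The change makes an imbalance in duration visible; it does not adjust the subgroup comparisons for it, and the report should say so.

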8 DATA MONITORING AND CONTROL

8.1 Centralised monitoring and controls

Monitoring of the study will be performed by ITEC Services, which will ensure, through regular communication (follow-up telephone calls and/or sending out newsletters) that the study is being conducted in accordance with the protocol and the regulatory requirements.

Monitoring visits will be conducted in 10% of active sites. The objective of these visits will be to validate the existence of the patients included in the study, and to check that the data reported in the CRF are consistent with the available source data. Monitoring visits will be described in the study monitoring guide and a monitoring report will be prepared after each visit.

The first questionnaires from each site will be monitored upon reception to ensure that the completion method is correct and that a follow up training is not necessary.

A specific Freephone number will be available for physicians having any questions related to the study.

Requests for corrections will be sent by Data Management for missing or erroneous CRF data on a regular basis, according to the Data Management Plan of the study. They will be transmitted to the Epidemiology Research Associate, who will manage the resolution with the physician through the eCRF, followed by emails and phone calls if necessary.

The monitoring procedures will be validated by CPF.

In addition, a Data Review Meeting will take place prior to the final statistical analysis. Decisions made during this meeting will be validated by the study Scientific Committee.

